## 2 STUDY DESCRIPTION

### 2.1 Study Design

This randomized, multicenter (ie, approximately 200 global centers), open-label, non-inferiority Phase 3 study is designed to evaluate the efficacy and safety of acalabrutinib (ACP-196) versus ibrutinib in subjects with relapsed or refractory chronic lymphocytic leukemia (CLL) who have high-risk prognostic markers (eg, 17p del and/or 11q del) per National Comprehensive Cancer Network (NCCN) guidelines ([NCCN Version 1. 2016](#)).

Approximately 500 eligible subjects will be randomized in a 1:1 ratio into 2 arms to receive either acalabrutinib 100 mg BID (Arm A; N=250) or ibrutinib 420 mg QD (Arm B; N=250).

This study will use an Interactive Web Response System (IWRS) for randomization. Randomization will be used to minimize bias in the assignment of subjects to treatment groups, to increase the likelihood that known and unknown subject attributes (eg, demographic and baseline characteristics) are evenly balanced, and to enhance the validity of statistical comparisons across treatment groups.

Randomization will be performed stratified by the following factors:

- Presence of 17p del
- Eastern Cooperative Oncology Group (ECOG) performance status (ECOG = 2 versus ECOG ≤1)

- Number of prior therapies (1-3 versus  $\geq 4$ )

An independent DMC will be formed and constituted according to regulatory agency guidelines. Detailed information regarding the composition of the DMC and detailed DMC procedures will be provided in a separate charter. The DMC will review the safety data periodically and provide recommendations according to the charter.

## **2.2 Study Objectives**

### **2.2.1 Primary Objective**

To assess whether acalabrutinib is non-inferior to ibrutinib with respect to progression free survival (PFS), based on Independent Review Committee (IRC) assessment, in subjects with relapsed or refractory CLL with high-risk prognostic markers.

### **2.2.2 Secondary Objectives**

#### **2.2.2.1 Efficacy Objectives**

To evaluate the benefit:risk of acalabrutinib versus ibrutinib in terms of:

- Grade  $\geq 3$  infections
- Richter's transformation
- Atrial fibrillation
- Overall survival (OS)

#### **2.2.2.2 Safety Objective**

The safety and tolerability including adverse events (AEs) of interest and laboratory assessments

### **2.2.3 Exploratory Objectives**

CCI [REDACTED]

[REDACTED]

[REDACTED]

[REDACTED]

[REDACTED]

[REDACTED]

[REDACTED]

[REDACTED]

[REDACTED]

### 2.3 Non-Inferiority (NI) Margin and Sample Size Justification

The NI margin of [CCI], with regard to median PFS, was selected to ensure that the efficacy of acalabrutinib will not be substantially inferior to ibrutinib in the event of a positive statistical outcome for the study. Assuming the median PFS for the ibrutinib arm is [CCI], and the time-to-event is exponentially distributed, a [CCI] in median PFS would be [CCI] for acalabrutinib.

The [CCI] for median PFS translates into a hazard ratio (HR) scale margin of 1.429, which was selected using the fixed margin method described in the U.S. Food and Drug Administration (FDA) Guidance for Industry: Non-Inferiority Clinical Trials (2010). This method, which is also in line with Committee for Medicinal Products for Human Use (CHMP) Guidance on the Choice of the Non-inferiority Margin (2005), uses a 2-step procedure to select the NI margin:

1. Determine  $M_1$  (as per FDA terminology), the entire effect of the active control (ibrutinib) assumed to be present in the NI study from historical data;
2. Determine  $M_2$  (as per FDA terminology), the largest clinically acceptable difference (degree of inferiority) of the test drug (acalabrutinib) compared to the active control (ibrutinib).

As the FDA Guidance describes,  $M_2$ , the pre-specified NI margin the non-inferiority study should meet, must never be greater than  $M_1$ .

Ofatumumab is currently used for the treatment of patients with CLL ([NCCN Version 2.2015](#)). In the RESONATE study ([Byrd 2014a](#)), ibrutinib demonstrated superiority over ofatumumab in PFS in an all-comers setting as well as in patients in the high-risk 17p del and 11q del populations. The primary results of the study are summarized in [Table 1](#) and provide the basis for choosing the NI margin.

**Table 1. Ibrutinib Data from RESONATE Study (Byrd 2014a)**

	Sample size	[CCI]
All patients	391	[CCI]
17p del	127	[CCI]
11q del	122	[CCI]

$M_1$ , calculated as [CCI] is estimated to be [CCI]. The [CCI] is used to account for the lack of information on study-to-study variability from a single historical study. The [CCI] translates into the [CCI]

Based on the median PFS for subjects with 17p del or 11q del treated with ibrutinib in the Phase 2 study (Byrd 2014b), we assume the median PFS of ibrutinib (based on IRC assessment) in this study will be approximately [CCI]. As described above the [CCI] on median PFS translates into a HR of 1.429 ( $M_2$ ) for acalabrutinib versus ibrutinib. The selected  $M_2$  of 1.429 [CCI]

Assuming [CCI] for PFS and an NI margin of 1.429, a sample size of 500 subjects (randomized 1:1 to each of the 2 arms) will provide 80% power at a 1-sided, 0.025 significance level to test the non-inferiority hypothesis. The accrual period is assumed to be about [CCI] with a follow-up period of approximately [CCI] after the last subject enters the study. The calculation assumes over the course of the study, [CCI]. The NI test will be performed when approximately 250 PFS events have been observed. Based on these assumptions, the [CCI]

The sample size and power calculations were based on East 6 (Version 6.3.1), with use of the design “Two-Sample Test, Parallel Design, Logrank Given Accrual Duration and Study Duration.”

## 2.4 Interim Analysis

No interim analysis for efficacy is planned for this trial.

An independent DMC will monitor safety during the study on a regular basis. The committee will operate independently of the Sponsor and the clinical investigators. A DMC charter will describe the details regarding DMC membership, schedule and format of meetings, format for presentation of data, access to data, method and timing of providing safety reports to the DMC, and other issues relevant to committee operations.

The DMC members will use their expertise, experience, and judgment to evaluate the safety data from the trial and to recommend to the Sponsor whether the trial should

continue or be stopped early for safety. No formal statistical rules recommending early stopping for safety are planned.

## **2.5 Final Analysis**

The sponsor has monitored total number PFS events across treatment arms closely, where primary analysis for progression is based on IRC assessment. A CCI [REDACTED] [REDACTED] has been determined based on projection of the timing of planned 250 events have been reported in the database. Database lock will occur after all data through the data cutoff date have been entered and cleaned. The final analysis will be conducted based on final locked database which consists of all available data, including all available PFS events, up to the data cutoff date.

## **2.6 Multiplicity Adjustments**

The primary endpoint of the study is PFS. The hypothesis to be evaluated in the analysis of the primary efficacy endpoint is that acalabrutinib is not inferior to ibrutinib where non-inferiority is defined by a pre-specified margin. If the upper bound of the 2-sided 95% CI for the HR is below 1.429, ACP-196 will be concluded to be non-inferior to ibrutinib.

The gate-keeping strategy will be implemented to control the family-wise error rate at the 0.05 level when performing multiple testing on primary and secondary endpoints. Specifically, if acalabrutinib is shown to be non-inferior to ibrutinib, the superiority of each of the secondary endpoints listed below will continue to be tested at a 2-sided 0.05 significance level in a pre-specified order until the statistical significance is not reached:

1. Incidence of atrial fibrillation
2. Incidence of grade  $\geq 3$  infections
3. Incidence of Richter's transformation
4. OS

Following the fixed sequence testing procedure, if a p-value is not statistically significant, the p-value for subsequent tests will be presented as descriptive.

The hierarchical order is determined according to estimated statistical power based on information from currently available data from ibrutinib studies and acalabrutinib studies.

## **2.7 Randomization and Blinding**

### **2.7.1 Randomization**

Randomization will be used to minimize bias in the assignment of subjects to treatment groups, to increase the likelihood that known and unknown subject attributes (e.g., demographic and baseline characteristics) are evenly balanced, and to enhance the validity of statistical comparisons across treatment groups.

Central randomization will be implemented through use of IWRS. Subjects will be randomized in a 1:1 ratio to receive either acalabrutinib or ibrutinib with the following stratification factors:

- Presence of 17p del (yes, no)
- ECOG performance status (ECOG = 2 versus ECOG  $\leq$ 1)
- Number of prior therapies (1-3 versus  $\geq$  4)

The randomization code will be controlled through a centralized procedure and will not be known to study and site personnel or the subject before the subject is randomized into the study.

### **2.7.2 Blinding**

In this open-label study, neither the subjects nor the investigators will be blinded to treatment. However, access to treatment randomization by IWRS will be controlled so that the sponsor's staff overseeing the conduct of the study or analyzing/summarizing data will not have aggregated efficacy or safety summary by randomized treatment arm before Sponsor unblinding for final analysis. Dummy treatment codes will be used to set up statistical programming prior to Sponsor unblinding for final analysis.

Response assessment will be performed centrally by the IRC. An Independent Review Charter for IRC will be created to describe details of data review, data flow, and work flow.

## **3 ANALYSIS POPULATIONS**

### **3.1 Intent-to-Treat Population**

The Intent-to-Treat (ITT) population is defined as all subjects randomized. All efficacy analyses will be performed using the ITT population and will be analyzed as randomized, following "intent-to-treat" principle, unless specified otherwise. In addition, the ITT

population will be used to summarize demographics, as well as baseline and disease characteristics.

### 3.2 Safety Population

The safety population includes all subjects who received at least one dose of study drug. The safety population will be the analysis population for safety analyses. Subjects will be analyzed as treated. If a subject incorrectly received both acalabrutinib and ibrutinib in any amount, the subject will be analyzed under the acalabrutinib arm, as a conservative approach.

### 3.3 Per Protocol Population

The per protocol (PP) population includes subjects in the ITT population with exclusion of:

- Subjects with < 75% relative dose intensity.
- Violated protocol inclusion or exclusion criteria that may affect interpretation of efficacy (Inclusion Criteria #3, #5, #6, Exclusion Criteria #2-4 and #6-9 in Protocol Amendment 5 dated 21 Oct 2020, and Inclusion Criterion #7 from Protocol Amendment 4 dated 14 Dec 2017).
- Received the incorrect treatment for  $\geq 7$  days.

### 3.4

CCI

CCI

## 4 GENERAL CONVENTIONS

Continuous data will be summarized using descriptive statistics (number of observations, mean, standard deviation, median, 25th and 75th percentiles, minimum, and maximum). Frequencies and percentages will be used for summarizing categorical (discrete) data.

Confidence intervals, when presented, will generally be constructed at the 2-sided 95% level. For binomial variables, the normal approximation methods will be employed unless otherwise specified.

Calculation of time to event or duration of event endpoints will be based on the study day of the event or censoring date rather than visit number or visit label. Missing efficacy or safety data will not be imputed unless otherwise specified.

The following rules will be used for the days to months/years conversion:

- 1 month=30.4375 days
- 1 year=365.25 days.

All summaries will be presented by treatment arm unless otherwise specified. Data will be presented in data listings by treatment arm and subject number.

## **4.1 Definitions**

### **4.1.1 Definition of Baseline and Post-Baseline Value**

For safety parameters, baseline is defined as the last measurement taken prior to the first dose of study drug. A post-baseline value is defined as a measurement taken after the first dose of study drug.

For efficacy parameters, the baseline value is defined as the last measurement taken prior to or on the date of randomization; a post-baseline value is defined as a measurement taken after the date of randomization.

The baseline and post-baseline definitions for laboratory parameters are similarly defined as those for safety parameters. For laboratory parameters used for response assessment, baseline values will be defined in reference to first dose date of study drug.

For assessments on the day of first dose where time is not captured, a nominal pre-dose indicator, if available, will serve as sufficient evidence that the assessment occurred prior to first dose. Assessments on the day of first dose where neither time nor a nominal pre-dose indicator are captured will be considered prior to first dose if such procedures are required by the protocol to be conducted before first dose.

For subjects who were not treated, the baseline is defined as the last valid assessment on or before date of randomization within the study.

### **4.1.2 Definition of Study Day**

For efficacy data summary, the study day will be calculated in reference to the date of randomization. Study Day 1 for efficacy data is defined as the date of randomization. For visits (or events) that occur on or after randomization, study day is defined as (date of visit [event] – date of randomization + 1). For visits (or events) that occur prior to randomization, study day is defined as (date of visit [event] – date of randomization).

For safety data, study day will be calculated in reference to the first dose date of study drug. Study Day 1 for safety data analysis is defined as the first dose date of study drug. For visits (or events) that occur on or after first dose date, dose day is defined as (date of visit [event] – date of first dose of study drug + 1). For visits (or events) that occur prior to first dose date, dose day is defined as (date of visit [event] – date of first dose of study drug).

#### **4.1.3 Definition of Prior and Concomitant Therapy**

For the purpose of inclusion in prior and/or concomitant medication or therapy tables, incomplete medication or radiation start and stop dates will be imputed as detailed in Section 4.2. Based on imputed start and stop dates:

- Prior medications/procedures/radiation therapies are defined as medications with a start date occurring before the date of first dose of study drug.
- Concomitant medications/procedures/radiation therapies are defined as medications that:
  - Had start date between the first dose date of study drug, 30 days after the last dose of study drug, or the first dose date of new anticancer therapy for CLL, whichever is earlier, or
  - Had start date before first dose date and stopped or continued after first dose date.
- In addition, medications/procedures/radiation therapies that meet the criteria for both prior and concomitant medications will be classified as both prior and concomitant medication.

#### **4.1.4 Prior and Subsequent Anticancer Therapy for CLL**

For the purpose of inclusion in the prior and/or subsequent anticancer therapy tables, incomplete medication start dates will be imputed as detailed in Section 4.2. The start date of anticancer therapy is defined as the first dose date of the therapy. Based on imputed start dates:

- Prior anticancer therapies are defined as medications that had an indication for the primary malignancy CLL and had a start date occurring before the date of first dose of study drug.
- Subsequent anticancer therapies are defined as medications that had an indication for the primary malignancy CLL and had a start date after the date of last dose of study drug.

#### **4.1.5 Time on Study**

Time on study will be calculated from the date of randomization to the study exit date, as follows:

Time on study = study exit date - date of randomization + 1 day.

#### **4.1.6 Treatment Emergent Period**

The treatment emergent period is defined as the period of time from the date of the first dose of study drug through 30 days after the date of the last dose of study drug or the first date starting new anticancer therapy for CLL, whichever is earlier.

### **4.2 Imputation Rules for Missing and Partial Data**

In general, other than for partial dates, missing data will not be imputed and will be treated as missing. The algorithms for imputation of partial dates vary depending upon the parameter.

#### **4.2.1 Adverse Events, Concomitant Medications, Prior/Subsequent Anticancer Therapies, Initial Diagnosis**

Imputation of partial dates will be made for AE onset and stop dates, start and end dates of concomitant medication, start date of prior/subsequent anticancer therapy, and date of initial diagnosis. If dates are completely missing, no imputation will be made. For any partial date with missing year, no imputation will be made.

The general rule for imputation is:

- If only day is missing, then the 15th of the month will be used.
- If only year is present, then June 30th will be used.

If such imputed date for initial diagnosis or prior anticancer therapy is on or after date of randomization, then date of randomization – 1 will be used. If such imputed date for

subsequent anticancer therapy is before date of last dose, then date of last dose + 1 will be used.

If the imputed date is for an AE start date and is in the same year and month as but before the first dose date, then the first dose date will be used, or if the imputed AE start date is after the AE end date, then the AE end date will be used. If the imputed date is for an AE start date and is in the same year and month as but after the last dose date + 30 days, then the last dose date + 30 days will be used.

If the imputed date is for an AE end date and is after the death date, then the death date will be used, or if the imputed AE end date is before the AE start date, then the AE start date will be used.

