Routine clinical assessments include physical exams, recording of symptoms, and hematologic evaluations to evaluate for both AEs and for disease progression at times when the CT scan is not obtained. If a subject shows signs of progression, the subject may continue treatment until

progression is confirmed by the IRC. The Investigator should report any suspected disease progression to the Sponsor or designee. Subjects should continue to be followed and adhere to study-related procedures until progression has been confirmed by the IRC regardless of the administration of subsequent anticancer therapy. New anticancer therapy should be withheld if clinically appropriate in the absence of IRC-confirmed progressive disease. In addition, laboratory assessments for disease progression will need to be confirmed by the central laboratory.

Overall Response Evaluations

Overall response assessments will include evaluation of physical exams, recording of symptoms, hematologic evaluations (Note: CBC with differential must be done within 7 days and bone marrow aspirate/biopsy [when applicable] must be done within 4 weeks of the contemporaneous radiographic evaluation), and radiographic evaluations per the schedule of assessments. Subjects who have signs and symptoms of progression outside of the scheduled assessment, should be evaluated by the investigator with a physical exam and a CBC with differential to determine if disease progression is present. Any suspected case of disease progression should be confirmed with a CT scan if one was not obtained and should be reported to the Sponsor or designee. Subjects may continue study treatment until progression is confirmed by a serial exam at least 2 weeks later. In addition, when clinically appropriate, based on investigator perceived risk:benefit assessment, a subject may continue treatment until progression is confirmed by the IRC, unless considered medically contraindicated. New anticancer therapy should be withheld if clinically appropriate in the absence of confirmed progressive disease by the IRC. The blood samples for response or disease progression determination are to be confirmed by a central laboratory (samples from local laboratories can be used if central testing is unavailable).

Early Termination (ET) Visit/Safety Follow-up (SFU) Visit

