9.3 DETERMINATION OF SAMPLE SIZE

A recently completed trial that studied PFS in CLL (Byrd 2014) showed that ibrutinib (the reference/comparator drug in Protocol ACE-CL-006) was superior to ofatumumab, a drug approved for the treatment of CLL in patients with previously treated CLL. Superiority in that study was shown in the overall study population (HR=0.21) as well as in patients with 17p del (HR=0.25) or 11q del (HR=0.14).

Protocol ACE-CL-006 is designed to have 80% power to show that the upper bound of a 2-sided 95% CI for PFS is < 1.429 (the NI bound).

With randomization in a 1:1 ratio, the trial will require approximately 250 events if acalabrutinib and ibrutinib are truly equally effective. Assuming an enrollment period of about [CCI] and a follow-up period of approximately [CCI] after the last subject enters the study, the estimated sample size is 500 subjects (250 per arm).

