## 7.1 Primary Efficacy Endpoint and Analysis

### 7.1.1 Primary Efficacy Endpoint

The primary efficacy endpoint is PFS as assessed by IRC, defined as the time from date of randomization to the date of first IRC-assessed disease progression or death due to any cause.

Subjects who do not have an IRC confirmed disease progression or death at or prior to data analysis cutoff date will be censored as follows:

**Table 2.** Primary Efficacy Analysis of PFS-IRC Outcome

Situation	Date of Event or Censoring	Outcome
Situation 1: PFS events include death or first IRC-confirmed disease progression that occurred at or prior to the data analysis cutoff date. Date of event is defined as follows:		
Death before first disease assessment	Date of death	Event
IRC-confirmed PD or death between scheduled assessments	Earliest date of IRC confirmed PD or death	Event
Situation 2: All other cases not meeting Situation 1 will be censored as follows:		
No baseline assessments	Randomization	Censored
No adequate post-baseline assessment	Randomization	Censored
No IRC-confirmed PD or death at the time of data cutoff	Date of last adequate IRC assessment before data cutoff	Censored
No IRC-confirmed PD or death before lost to follow-up or study exit	Date of last adequate IRC assessment before lost to follow-up or study exit	Censored
No IRC-assessed PD or death before start of subsequent anticancer therapy	Date of the last adequate IRC assessment before start of subsequent anticancer therapy	Censored

Situation	Date of Event or Censoring	Outcome
IRC-assessed PD or death after start of subsequent anticancer therapy	Date of the last adequate IRC assessment before start of subsequent anticancer therapy	Censored
IRC-confirmed PD or death immediately after 2 or more consecutively missed visits	Date of last adequate IRC assessment before the consecutively missed visits	Censored

PD=progressive disease; IRC=independent review committee.

PFS will be calculated as date of disease progression or death (censoring date for censored subjects) – randomization date + 1.

The adequate IRC assessment is defined as the IRC-assessed overall response that is not 'UNK' (unknown), as defined in the IRC charter.

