### 7.1.2 Primary Efficacy Analysis

The primary analysis, which is event-based, will be conducted after enrollment is completed and approximately 250 IRC events have been observed in the study. A summary of PFS events will be provided by treatment arm.

The estimate of the hazard ratio (acalabrutinib/ibrutinib) and its corresponding 95% CI will be computed using a Cox Proportional Hazards model stratified by the randomization stratification factors (collapsed if necessary, according to Section 7). Randomization stratification factors will be based on IWRS randomization assignment.

If the upper bound of the 2-sided 95% CI for the HR is below 1.429, acalabrutinib will be concluded to be non-inferior to ibrutinib.

Kaplan-Meier (KM) curves will be presented by treatment arm and the KM method will be used to estimate the distribution of PFS (quartiles and median with 95% CIs, minimum, and maximum). The proportion of subjects who are progression free and the corresponding 95% CI will be estimated based on KM method at select timepoints (e.g., 6, 12, 18, 24, 30, 36 months, etc.) by treatment arm.

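### SAP 4.2.1 checks a partial new-therapy start date only against last dose, so Table 2 can wrongly censor or wrongly keep a PFS event, and Table 2 has no new-therapy definition of its own

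*SAP*

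**What the plan says.** SAP 4.2.1 imputes a subsequent-therapy start with only the day missing to the 15th of the month, and one with only the year known to 30 June. One correction follows: if the imputed date for "subsequent anticancer therapy is before date of last dose, then date of last dose + 1 will be used". The same section checks imputed AE dates against first dose, last dose plus 30 days, the other AE date and death. No such check against progression or death exists for the new-therapy date.

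SAP 7.1.1, Table 2, contains the row "IRC-assessed PD or death after start of subsequent anticancer therapy". The outcome there is censored at the last adequate IRC assessment before the therapy began. The resulting PFS times feed the primary decision: "If the upper bound of the 2-sided 95% CI for the HR is below 1.429, acalabrutinib will be concluded to be non-inferior to ibrutinib".

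SAP 4.1.4 calls a CLL-indicated therapy subsequent if it "had a start date after the date of last dose of study drug". That section introduces its definitions for the prior and subsequent therapy tables. Table 2 does not cite it, and Section 7.1.1 supplies nothing else.

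On expected order, Protocol 7.1 says: "New anticancer therapy should be withheld if clinically appropriate in the absence of confirmed progressive disease by the IRC". Protocol Section 4 follows subjects who have stopped study drug for progression or death.

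**The concern.** The last-dose correction protects a subject who was still taking drug at progression. It does not protect one who stopped earlier. Suppose drug stops in January for an adverse event, the IRC dates progression at 20 March, and new therapy truly begins on 27 March but is recorded only as March. The start becomes 15 March, progression then appears to follow new therapy, and Table 2 censors a genuine event. The order of events was the one the protocol expects.

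The error also runs the other way. If therapy is recorded as March and the subject dies on 10 March, the start becomes 15 March, after death. The therapy must have come first, so Table 2's own rule calls for censoring, yet the death is kept as an event.

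The second gap is the definition. If 4.1.4 governs Table 2, a randomized but never-dosed subject has no last dose and so can have no subsequent therapy. CLL therapy begun on or before the last dose day is not covered either. If 4.1.4 does not govern Table 2, the censoring trigger is undefined.

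At stake is whether individual primary-endpoint outcomes are decided by a date convention. The subjects exposed are mainly those who stopped drug before progressing, a group whose size could differ by arm.

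**Working it through.** **Planned size.** The inputs are the margin 1.429, 1:1 allocation and a true HR of 1. The design "will provide 80% power at a 1-sided, 0.025 significance level to test the non-inferiority hypothesis", and "the trial will require approximately 250 events if acalabrutinib and ibrutinib are truly equally effective" (Protocol 9.3). Schoenfeld: 4 × (1.960 + 0.842)² / (ln 1.429)² = 246.4, so 247 events. Freedman's form gives 252. Power at 250 events is 80.6%. The plan's figure reproduces.

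**Which subjects are exposed.** Every calendar day of a non-leap year was taken as the true therapy start, with progression 1 to 60 days earlier and last dose on or after progression. Of 667,950 combinations, none was wrongly censored under either imputation rule. Wrongful censoring therefore requires last dose to precede progression. A short interval is enough: with last dose 18 March, progression 20 March and therapy recorded as March, the 15th is moved to 19 March and the progression is still censored.

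**Day missing, progression first, both dates in one 30-day month, subject already off drug.** The event is lost when progression falls on day 16 or later.
- Random days: C(15,2) / C(30,2) = 105/435 = 24.1%.
- 7-day gap: progression can fall on days 1–23 and is lost on days 16–23, so 8/23 = 35%.
- 14-day gap: progression can fall on days 1–16 and is lost on day 16 only, so 1/16 = 6%.
- More than 15 days: impossible even in a 31-day month, because day 16 plus 15 is already day 31.

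**Reverse error in the same setting.** When therapy truly came first, the event is wrongly kept if progression or death falls on day 15 or earlier. With random days this is again C(15,2) / C(30,2) = 24.1%.

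**Without the same-month condition** (all calendar days equally likely; the gaps are assumptions):

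| Error | Gap, days | Day missing | Year only |
|---|---|---|---|
| Progression first, wrongly censored | 1–14 | 26% | 48% |
| | 1–30 | 12% | 46% |
| | 1–90 | 4% | 38% |
| Therapy first, wrongly kept | 1–30 | 12% | 45% |
| | 1–90 | 4% | 37% |

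**Illustrative effect on power if events are lost and not replaced:** 2 lost, 80.3%; 5 lost, 79.8%; 10 lost, 79.0%; 25 lost, 76.3%.

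**The case against.** The case for leaving the text alone has real force. The error needs a partial date, a subject already off drug, and progression close to the switch. Protocol 7.1 asks sites, where clinically appropriate, to wait for IRC confirmation, which argues against very short gaps. It also collects subsequent therapies about every 12 weeks, so year-only dates look unlikely. Misclassification runs both ways at similar rates. SAP 7.1.3 already plans an analysis that ignores subsequent therapy and so cannot be affected by this date. All of that stands and limits the size. But the sensitivity analysis does not correct the primary estimate. It also ignores correctly dated switches, so a difference between the two results would not isolate the imputation.

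Three stronger readings are tempting and are not supported:
- *Radiotherapy for CLL escapes because 4.1.4 speaks of medications.* SAP 4.1.3 uses medications as the umbrella word for procedures and radiation too.
- *The imputed date distorts the treatment-emergent window in the example above.* SAP 4.1.6 closes that window at the earlier of last dose plus 30 days and new therapy. After a January stop it has closed by 2 March, so an imputed 15 March changes nothing.
- *The rule favours one arm or a non-inferiority finding.* The documents give no count of partial dates by arm and no direction.

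The link from 4.1.4 to Table 2 is likewise an inference. It is the only definition available, not one that Table 2 invokes.

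**Conclusion.** The point holds as a correctable defect of limited size. As written, the imputation rule can reverse the true order of progression and new therapy, or place therapy after death, and Table 2 then returns the wrong outcome. The conditional rates for a missing day are 24% (random days), 35% (7-day gap), 6% (14-day gap) and zero beyond 15 days. They assume a 30-day month, both dates in that month, progression first, and last dose early enough not to interfere. Neither the number of partial dates nor the actual gaps are in the documents, so no overall rate or bias in the HR can be stated. The overall effect is probably small: five lost and unreplaced events would move power from 80.6% to 79.8%. The absence of a PFS-specific definition of new therapy is a separate gap, certain on the text, affecting never-dosed ITT subjects and therapy begun by the last dose day.

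**What to change.** **SAP 4.2.1.** When only the day is missing, keep the imputed subsequent-therapy start:
- within the recorded month;
- not before last dose + 1;
- not before IRC progression + 1, if progression falls in that month;
- not after death or the data cutoff.

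State that the upper limits prevail where limits conflict. Apply the death cap as the day before death, because a start equal to the death date would still leave the death not later than the start. For year-only dates keep the present rule and add only the death and cutoff caps. Forcing such a start after any progression in the same year would let the outcome dictate the date across many months.

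**SAP 7.1.1.** Define new therapy for PFS censoring as any non-study CLL-directed therapy started after randomization, whether or not a last dose exists. Acalabrutinib or ibrutinib given as study drug should not count, so that dispensing of the wrong arm's drug does not trigger censoring.

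**Reporting.** Give, by arm, the number of PFS outcomes whose event or censoring status depends on an imputed therapy date.

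**Cost.** A few lines of SAP text and programming, settled before unblinding. The event target is unchanged. The downside is that a few progressions that truly followed new therapy in the same month may be kept as events. The SAP 7.1.3 analysis that disregards subsequent therapy shows how much this matters.
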